8.6.1. Stopping Rules for Liver Chemistry Elevations

All cases of confirmed laboratory results meeting any of the following criteria, but having an alternative etiology such as congestive heart failure, introduction of a new drug, some identified biliary tract issues etc., must be reviewed by local hepatologist, the DSMB hepatologist, and the decision to restart the Study Drug must be made upon reaching a general agreement between consulting hepatologist, the DSMB hepatologist, and the Sponsor Medical Monitor that the alternative etiology is well supported as the likely cause, and when ALT and AST levels become

\leq 3 × ULN. Until this evaluation is completed and a decision agreed upon, the treatment with the Study Drug will remain interrupted.

In the event of confirmed laboratory results meeting any of the following criteria, **and the event is without an alternative explanation as discussed with the Medical Monitor**, dosing of a patient with Study Drug (ISIS 678354 or placebo) will be stopped permanently; values that are not confirmed due to failure to retest or missing lab values will be presumed confirmed:

- 1. ALT or $AST > 8 \times ULN$, which is confirmed
- 2. ALT or AST > 5 × ULN, which is confirmed and persists for \ge 2 weeks
- 3. ALT or AST > $3 \times$ ULN (or the greater of $2 \times$ baseline value or $3 \times$ ULN if the baseline value was > ULN), which is confirmed **and** total bilirubin > $2 \times$ ULN or INR > 1.5
- 4. ALT or AST > 3 × ULN (or the greater of 2 × baseline value or 3 × ULN if the baseline value was > ULN), which is confirmed, **and** the new appearance (i.e., onset coincides with the changes in hepatic enzymes) of fatigue, nausea, vomiting, right upper quadrant pain or tenderness, fever, rash, and/or concomitant eosinophilia (> ULN)

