The number and percent of patients falling in each of the following categories based on results after first dose will be tabulated by treatment group. The risk different (95% CI) in the crude incidence rates between each active treatment group (or total ISIS 678354) and pooled placebo group will be provided for selected categories.

- ALT or AST \geq ULN
- The higher of ALT/AST \ge 3 × upper limit of normal (ULN) or ALT/AST \ge 2 × Baseline (i.e., ALT/AST \ge 3 × ULN and ALT/AST \ge 2 × Baseline)
- ALT/AST \geq 3 × ULN
- ALT/AST \geq 5 × ULN
- ALT/AST $\geq 8 \times ULN$
- $ALT/AST \ge 10 \times ULN$
- ALT/AST $\geq 20 \times ULN$
- Highest ALT falling in: ≥ 3 × ULN < 5 × ULN, ≥ 5 × ULN < 10 × ULN, ≥ 10 × ULN -< 20 × ULN (the risk difference will not be provided for this category)
- Total bilirubin $\geq 2 \times ULN$
- Total bilirubin $\geq 5 \times ULN$
- Total bilirubin $\ge 8 \times ULN$
- ALT or AST \geq 3 × ULN and Total bilirubin \geq 2 × ULN
- $ALP \ge 2 \times ULN$ and (baseline $ALP < 2 \times ULN$ or baseline ALP missing)
- Direct bilirubin $\ge 2 \times ULN$
- Direct bilirubin $\geq 5 \times ULN$

- GGT $\ge 2 \times ULN$
- ALT \geq 3 × ULN and INR \geq 1.5
- $ALP \ge 2 \times ULN$
- ALP \geq 3× ULN
- INR $\geq 1.5 \times ULN$
- INR \geq 3 × ULN
- INR \geq 5 × ULN

The number and percent of patients falling in each of the following categories based on confirmed results after first dose will be tabulated by treatment group (a confirmed value is based on a consecutive lab value performed on a different day to, but within 10 days of, the initial value. If that value is in the same or worse category then the initial value is confirmed. If the consecutive value is in a better category then the initial value is confirmed using the consecutive value category. If there is no retest within 10 days then the initial value is presumed confirmed. If there are multiple results on the same day, then the worst value will be utilized in the analysis):

- The higher of ALT/AST \ge 3 × ULN or ALT/AST \ge 2 × Baseline, which is confirmed
- ALT/AST \geq 3 × ULN, which is confirmed
- ALT/AST \geq 5 × ULN, which is confirmed
- ALT/AST $\geq 10 \times$ ULN, which is confirmed
- ALT/AST $\geq 20 \times$ ULN, which is confirmed

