For patients having at least 3-fold or greater elevations above the ULN for ALT or AST or for patients with baseline ALT or AST \geq ULN at least 2-fold increases from Baseline, spaghetti plots and a listing of all of the ALT, AST, total bilirubin, direct bilirubin, INR, and ALP records will be provided.

For patients having elevation in liver enzymes (ALT \ge 3 × ULN), the time to onset of the first event will be summarized using descriptive statistics

Other liver abnormalities including elevation of ALT ($\ge 3 \times ULN$) accompanied by INR ≥ 1.5 , elevation of ALT ($\ge 3 \times ULN$) accompanied by elevated total bilirubin $\ge 2 \times ULN$ and ALP $\ge 2 \times ULN$ will be reviewed by the study team and summarized if needed.

Additionally, evaluation of Drug Induced Serious Hepatoxicity (eDISH) plots by treatment group will be provided for liver safety parameters (AST, ALT, Total bilirubin and ALP).

Renal Laboratory Abnormalities:

The number and percent of patients falling in each of the following categories based on results at a) any time after first dose) and b) the final visit will be tabulated by treatment group. The risk different (95% CI) in the crude incidence rates between each active treatment group (or total ISIS 678354) and pooled placebo group will be provided.

- Serum creatinine $\geq 0.3 \text{ mg/dL}$ higher than baseline
- Serum creatinine $\geq 50\%$ higher than baseline

ISIS 678354-CS3

Statistical Analysis Plan

A listing of the creatinine values over time will be provided for each patient meeting either of the two criteria.

The number and percent of patients falling in each of the following additional categories based on results at any time after first dose will also be tabulated by treatment group. The risk different (95% CI) in the crude incidence rates between each active treatment group (or total ISIS 678354) and pooled placebo group will be provided.

- Serum creatinine $\geq 2.0 \times$ baseline, and $\geq 3.0 \times$ baseline
- eGFR reduction from baseline, $\geq 25\%$, $\geq 30\%$, $\geq 50\%$, and $\geq 75\%$
- UACR $\ge 300 \text{ mg/g}$, $\ge 500 \text{ mg/g}$, $\ge 600 \text{ mg/g}$, $\ge 1200 \text{ mg/g}$
- UACR increase from Baseline $\geq 50\%$
- UPCR \geq 500mg/g, \geq 1000 mg/g, \geq 2000 mg/g

A listing of creatinine and eGFR will be provided for those patients having \geq 2-fold elevation above baseline in creatinine or \geq 50% decrease from baseline in eGFR.

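### The SAP's enzyme-plus-INR row counts ALT only, while the protocol's stopping criterion and the SAP's own bilirubin row count ALT or AST

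*Combined protocol and SAP*

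**What the plan says.** **Protocol 8.6.1 (Stopping Rules for Liver Chemistry Elevations), criterion 3.** The enzyme part is "ALT or AST > $3 \times$ ULN (or the greater of $2 \times$ baseline value or $3 \times$ ULN" where the baseline was above ULN. The second part is "which is confirmed and total bilirubin > $2 \times$ ULN or INR > 1.5". If the result is confirmed and no alternative explanation is found, "dosing of a patient with Study Drug (ISIS 678354 or placebo) will be stopped permanently". A result that is not retested is presumed confirmed.

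**SAP 4.10.5 (Clinical Laboratory Evaluation), hepatobiliary categories.** These are tabulated by treatment group. The two halves of criterion 3 appear as separate composites:

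- the bilirubin half: "ALT or AST \geq 3 × ULN and Total bilirubin \geq 2 × ULN";
- the INR half: "ALT \geq 3 × ULN and INR \geq 1.5".

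The same section has rows for ALT/AST alone at several multiples of ULN, confirmed versions such as "ALT/AST \geq 3 × ULN, which is confirmed", and rows for INR alone that start at 1.5 × ULN.

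A later sentence in the section begins "Other liver abnormalities including elevation of ALT". It names ALT ≥ 3 × ULN with INR ≥ 1.5 among the items that the study team will review and summarise if needed. AST is not mentioned there.

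**The concern.** The SAP splits one protocol criterion into two rows and carries AST into only one of them. It gives no reason for the difference. Elsewhere in the section, the plain enzyme rows and the trigger for the patient listing accept either enzyme, so the INR composite differs from the rest of the SAP as well as from the protocol.

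The row reports how many patients in each treatment group had a transaminase rise together with a raised INR. If an AST-driven case occurs, the row will not count it, although the protocol's laboratory criterion was met. In a trial of this size, one patient is enough to change what the row reports.

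**Working it through.** The documents state no figure to reproduce, so the check compares definitions and then runs example patients through them.

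**Step 1. Definitions side by side.** I read ALT/AST in the SAP as either enzyme.

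| Source | Enzyme part | Second part |
|---|---|---|
| Protocol 8.6.1, criterion 3 | ALT or AST > 3 × ULN, confirmed | bilirubin > 2 × ULN or INR > 1.5 |
| SAP 4.10.5, bilirubin composite | ALT or AST ≥ 3 × ULN | bilirubin ≥ 2 × ULN |
| SAP 4.10.5, INR composite | ALT ≥ 3 × ULN | INR ≥ 1.5 |
| SAP 4.10.5, review item | ALT ≥ 3 × ULN | INR ≥ 1.5 |

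The SAP also uses ≥ where the protocol uses >. Its composites have no confirmation requirement and no baseline-adjusted branch. Those differences make the SAP rows more inclusive, so they do not cause an undercount. Dropping AST does.

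**Step 2. Example patients.** Enzymes and bilirubin are in multiples of ULN, and INR is absolute. Baseline enzymes are assumed normal and the result confirmed. The documents do not give the laboratory's INR upper limit. I assume 1.1 to 1.2, so the INR-alone cut is 1.5 × 1.1 = 1.65 to 1.5 × 1.2 = 1.80.

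| | A | B | C | D |
|---|---|---|---|---|
| ALT | 2 | 2 | 2 | 4 |
| AST | 4 | 4 | 4 | 4 |
| Bilirubin | 1 | 1 | 2.5 | 1 |
| INR | 1.6 | 1.9 | 1.6 | 1.6 |
| Protocol criterion 3 (laboratory part) | met | met | met | met |
| SAP ALT/AST ≥ 3 × ULN | 1 | 1 | 1 | 1 |
| SAP bilirubin composite | 0 | 0 | 1 | 0 |
| SAP INR composite, as written | 0 | 0 | 0 | 1 |
| SAP INR alone ≥ 1.5 × ULN | 0 | 1 | 0 | 0 |
| INR composite with ALT or AST | 1 | 1 | 1 | 1 |

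Patients A to C meet criterion 3 and score zero in the INR composite. Patient C is caught by the bilirubin composite. Patient B is caught by the INR-alone row, but without any link to the enzyme rise. Patient A appears only in the enzyme rows of this table. Adding AST brings all three into the row and leaves patient D unchanged.

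**Step 3. Size of one missed case.** The results summary gives 43 olezarsen patients, 22 of them on 80 mg. Exact (Clopper-Pearson) 95% limits:

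- 0 events in n: upper limit = 1 − 0.025^(1/n). For n = 43 this is 8.2%; for n = 22 it is 15.4%.
- 1 event in n: the upper limit p solves (1 − p)^n + n·p·(1 − p)^(n−1) = 0.025. For 1/43 = 2.3% it is 12.3%; for 1/22 = 4.5% it is 22.8%.

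These limits describe that one row only, and only if such a case occurs.

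**Step 4. Are the data there?** Protocol 8.5.1 requires at least weekly retesting, INR included, once ALT or AST above 3 × ULN is confirmed. SAP 4.2.4 admits unscheduled central-laboratory results to the abnormality summaries. The inputs for an AST-plus-INR count are therefore already planned.

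**The case against.** The strongest reply is that little is hidden. An AST-driven patient counts in the ALT/AST ≥ 3 × ULN row and, if confirmed or not retested, in the confirmed row. The AST shift tables and the eDISH plots include AST. The listing and spaghetti plots are triggered by ALT or AST and show INR beside the enzymes. SAP 4.10.4.8 also plans a summary of discontinuations with liver laboratory elevation. All of this is correct. A reader might infer that the case vanishes from the liver safety table; the documents do not support that, because the zero is confined to the INR composite row.

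Three further points stand. Risk differences are promised only for selected categories and this row is not named, so no distorted risk difference can be asserted. The study-team review list is open-ended, so an AST-driven case is not shut out of review, and Protocol 8.5.1 already sends ALT or AST alerts to the investigator and medical monitor. Protocol 5.1 allows oral anticoagulants, so INR ≥ 1.5 is not specific to the liver in this population.

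It can also be said that the table never claims to count stopping-rule cases: there are no rows for the two-week persistence or symptom criteria. That is true, and the protocol imposes no duty of exact correspondence. It does not explain why two adjacent composites in one table use different enzyme definitions.

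None of the other outputs supplies the missing count. The enzyme rows do not show INR, the INR-alone row uses a multiple of ULN rather than 1.5, the eDISH plots omit INR, and the discontinuation summary does not name INR. The listing shows the pair patient by patient but gives no count by treatment group.

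**Conclusion.** The inconsistency is in the text and is minor. As written, the INR composite undercounts patients with AST ≥ 3 × ULN, ALT < 3 × ULN and INR ≥ 1.5. Where bilirubin is also below 2 × ULN, no composite row counts them, and the joint enzyme-plus-INR count by treatment group is lost. The patient-level information is not lost.

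Few or no cases are expected, and the documents give no evidence that one occurred. The shift from 0/43 to 1/43 is conditional on a single case. The conclusion rests on reading ALT/AST as either enzyme. The statement that the INR-alone row can miss INR 1.6 rests on the assumed INR upper limit of 1.1 to 1.2.

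A permanent stop also needs confirmation, actual or presumed, and no alternative explanation, so meeting the laboratory values does not by itself mean that drug was stopped. A reader might extend the point to the ALT-only time-to-onset summary in the same section. That summary is descriptive and not tied to criterion 3, so restricting it to ALT is a reporting choice rather than a mismatch.

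**What to change.** In SAP 4.10.5, define the row as ALT or AST ≥ 3 × ULN and INR ≥ 1.5, parallel to the bilirubin composite. Make the same change to the enzyme-plus-INR item in the study-team review sentence.

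The cost is two small wording edits and one programming condition, with no new data. If the tables have already been produced, one supplementary row is enough. The change can only add qualifying patients to the row. It aligns reporting with the criterion as the protocol states it and leaves the clinical stopping rule untouched.

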4.10.6. Vital Signs and Physical Findings

Vital signs include:

- pulse rate (beats/minute)
- systolic and diastolic blood pressure (SBP and DBP) (mmHg)
- respiration rate (breaths/min)
- body temperature, measured under the arm pit (°C)
- weight
- BMI

Summary tables will be created to present the descriptive statistics for vital sign values as well as the change and percent change from Baseline at each study visit.

Number and percentage of subjects falling in each of the following categories will be tabulated by treatment group:

- Change from baseline in SBP > 5, > 10, > 15, > 20, > 30 mmHg
- Change from baseline in DBP > 5, > 10, > 15, > 20, > 30 mmHg
- Change from baseline in pulse > 5, > 10, > 15, > 20 bpm

A by-subject listing of vital signs will be provided.

Adverse changes in physical examinations that are deemed clinically significant by the Investigator will be classified as adverse events. Physical examination results will be listed.

4.10.7. 12-Lead Electrocardiograms (ECG)

ECGs will be performed in triplicate at the visits indicated in the protocol Schedule of Procedures. The ECG data will include ventricular rate, PR interval, QRS duration, QT, QTc intervals (machine reading), QTc interval calculated using Fridericia's formula (QTcF) and overall interpretation. For the continuous variables above, descriptive statistics of the average of triplicate results at each study visit, as well as the change and percent change from Baseline to each study visit, will be presented in summary tables; for the categorical responses to overall interpretation, the worst of triplicate results at each visit will be summarized by counts and percentages. All the data collected in triplicate will be listed. Following summary tables will be presented.

- A summary of each ECG parameter by treatment group and visit
- A summary of the number and percentage of subjects with QTcF interval exceeding the following predefined upper limit: > 450 ms, > 480 ms, > 500 ms. The average of triplicates will be used to categorize the data.
- Shift table from baseline to the worst (highest) post-baseline QTcF interval by treatment group. The categories for the shift table will be: $\leq 450 \text{ msec}$, > 450 msec to $\leq 480 \text{ msec}$, > 480 msec to $\leq 500 \text{ msec}$, and > 500 msec. The average of triplicates will be used to categorize the data.

• The number and percent of patients experiencing an increase from baseline in QTcF interval of greater than 30 msec or 60 msec at any time post-baseline will be summarized by treatment group. This analysis will be presented for all patients in the Safety set and also for the subgroup whose QTcF is normal at baseline. Normal QTcF is defined as ≤ 450 msec for males or ≤ 470 msec for females. The average of triplicates will be used to determine the increase.

ECG results will be listed.

4.10.8. Data and Safety Monitoring Board (DSMB)

A DSMB, also known as Data Monitoring Committee, will be assembled to review safety and tolerability data collected during this study. Based on its ongoing assessment of the safety and tolerability, the DSMB will provide recommendations to the Sponsor for modifying, stopping or continuing the study as planned. Details on the safety assessments, frequency of review, meeting schedules, and controlled access to unblinded data are outlined in the DSMB Charter.

4.11. Other Analyses

4.11.1. Pharmacokinetics

During the treatment period, blood samples for the determination of plasma ISIS 678354 concentrations will be collected from all patients prior to dosing.

 Table 2:
 Plasma Trough and Post-Treatment Sampling Schedule for all Patients

	Treatment Period												Follo	w-up	Period
Study Week		3	5	9	13	17		25/ET- L2*	29	37		53/ET-L5* or Tx ET	4**	8**	13/Post Tx ET**
Study Day	1	15	29	57	85	113	141	169	197	253	309	365	28**	56**	91**
		time		dose		dose	dose	Pre-dose and 2 hr ± 15 min	dose	-	Pre- dose	5	Any time	2	Any time

* Landmark visit. For early termination landmark (ET-L) visits: Week 25 is ET-L2 and Week 53 is ET-L5

** Weeks/days from end of treatment. End of treatment is defined as 1 dosing interval post-last dose

*** Samples can be collected within the \pm 15 min and \pm 30 min window, but the actual sampling time should be recorded accurately in eCRF

Plasma concentrations of ISIS 678354 (measured as total full-length oligonucleotides or ISIS 678354-eq, i.e., ISIS 678354-eq, including fully conjugated, partially conjugated, and unconjugated ISIS 678354), along with the scheduled (nominal) and actual sampling times (i.e., time from subcutaneous [SC] dosing) will be listed (when applicable) for each evaluable patient by treatment, actual dose, gender, subject ID, subject immunogenicity (IM) status and study day. Plasma concentrations below the lower limit of quantification (LLOQ) will be presented as "BLQ". In addition, percent differences between scheduled and actual sampling times will also be listed.

For all patients who receive ISIS 678354 treatment, ISIS 678354 plasma trough (pre-dose), peak (2 hr and 4 hr), and post-treatment (28, 56, 84, and 119 days after the last dose) concentrations will be summarized using descriptive statistics by treatment, dose, study day, and scheduled time point, with and without stratification by IM status (see Section 4.11.2). For the purpose of calculating typical descriptive statistics (n, mean, SD, %CV, geometric mean, geometric %CV, median, minimum and

Statistical Analysis Plan

maximum) for plasma concentrations, all below the lower limit of quantification (BLQ) values will be set to zero. Mean plasma concentrations that are BLQ will be presented as BLQ, and the SD and %CV, as well as geometric mean and geometric %CV, will be reported as "NA" (not applicable). At the discretion of the pharmacokineticist and/or biostatistician, samples may be excluded from descriptive statistics if there are large deviations between scheduled and actual sampling times (percent difference between scheduled and actual sampling time greater than 30%), or large deviations between actual dose and nominal dose (percent difference between nominal and actual dose greater than 30%). Any samples excluded from the summary descriptive statistics, if deemed necessary, will be listed separately along with the reason for exclusion.

For patients who receive ISIS 678354 treatment and not participating in the OLE, the plasma disposition half-life associated with the apparent terminal elimination phase will be calculated using a non-compartment method, if appropriate, using available data. Other PK parameters, as appropriate, may be determined or calculated at the discretion of the PK scientist. Plasma PK parameters will be summarized using descriptive statistics (n, mean, SD, %CV, geometric mean, geometric %CV, median, minimum, and maximum) by treatment and dose with and without stratification by IM status (see Section 4.11.2).

Population pharmacokinetics and covariate analysis may be performed, combined with data from other studies if deemed appropriate, and results, if generated, will be reported separately. Exposure-response relationships between selected pharmacokinetic and efficacy and safety measures may also be explored, where deemed appropriate.

4.11.2. Immunogenicity Analysis

4.11.2.1. Sample Level ADA Data

Samples collected for IM assessment at baseline (Day 1 pre-dose), during treatment and post-treatment follow-up period including early termination samples will be analyzed for anti-ISIS 678354 antibodies (ADA).

An evaluable sample will be designated 'Positive' based on both positive screening and confirmation assay results (i.e., confirmed positive result), and otherwise will be deemed 'Negative'. An unevaluable sample, for example, a sample not being stored properly, or insufficient volume for analysis, will be reported as "unknown". Sample ADA results (screen positive/negative, confirmed positive/negative or unevaluable, and when applicable, titer of anti-ISIS-678354 antibodies) before, during, and after treatment with study drug (ISIS-678354 or placebo) (sample ADA status) will be listed by treatment, dose, and day of collection.

The sample ADA incidence (number) and incidence rate (percent) at each evaluated study time point will be determined and appropriately summarized by treatment and dose as the total number of and percentage of evaluated subjects with sample ADA negative, positive, and unknown status. Furthermore, titer over time will be also appropriately summarized (using descriptive statistics) as median, quartiles (25% and 75%), and range by treatment and dose.

4.11.2.2. Subject Level ADA Data

Subject ADA status overall (ADASTAT) will be defined as 'Positive' status if they have at least one confirmed positive sample result at any time during the treatment or post-treatment evaluation periods; 'Negative' status if all evaluated ADA sample results during the treatment and post-treatment evaluation periods are ADA negative and they have at least one evaluable ADA result collected post-study drug treatment. Otherwise, a study subject will be assigned 'Unknown' ADA status.

Furthermore, subjects with positive overall ADA status may be further classified into different ADA types (ADATYPE) based on their baseline ADA status and change in ADA titer post treatment as described below (Shankar *et al.* 2014):

- Treatment-Emergent ADA: subjects with either treatment-induced ADA or treatment-boosted ADA as described below:
 - o Treatment-Induced ADA: ADA developed de novo (seroconversion) following study drug administration (i.e., formation of ADA any time after the initial drug administration in a subject without pre-existing ADA, i.e., baseline negative ADA).
 - o Treatment-Boosted ADA: pre-existing ADA that were boosted to a higher level following study drug administration (i.e., any time after the initial drug administration the ADA titer is greater than the baseline titer by a factor of 8-fold or more).
- Treatment-Unaffected ADA: pre-existing ADA that were not affected (boosted) following study drug administration (i.e., any time after the initial drug administration the ADA titer is 4-fold or less).
- For patients with negative overall ADA status, ADATYPE would be classified as baseline negative or baseline positive, based on their baseline ADA status.

Other subject level IM parameters to be calculated/defined may include but not limited to:

- ADA category (ADACAT) will include subjects with Negative, Treatment-Unaffected, and Treatment-Emergent ADA status as described above.
- Subject ADA Status at Baseline (ADASTATB): "Positive" if the subject has Week 1 Day 1 pre-dose sample (baseline) tested as confirmed positive; "Negative" if the subject has Week 1 Day 1 pre-dose sample (baseline) tested as negative; "Unknown" if the subject has Week 1 Day 1 pre-dose sample (baseline) unevaluable.
- First day of ADA detected (TFSTADA): i.e., the first day positive ADA sample was observed, will be calculated by: the date of first sample has "positive" sample IM status first dose date +1.
- Onset of treatment-emergent ADA (ONSETTE): i.e., the first day treatment-emergent ADA positive sample observed, and will be calculated for subjects with treatment-induced ADA and treatment-boosted ADA by:
 - For treatment-induced ADA: the date of first sample has "positive" sample IM status - first dose date +1.
 - For treatment-boosted ADA: the date of the first sample has ADA titer greater than the baseline titer by a factor of 8-fold or more first dose date +1.
- Last Positive ADA Study Day (TLSTADA): defined as the last positive ADA sample observed from the start of study drug treatment and will be calculated by: the date of last sample has "positive" sample IM status first dose date +1.
- Last IM Sampling Study Day (TLSTSAMP): defined as the last ADA sample collected from the start of study drug treatment and will be calculated by: the date of last sample colleted first dose date +1.

- Duration of treatment-emergent ADA (DURTE): i.e., the total duration of treatment-emergent ADA during the study, and will be calculated using the last sample result carried forward. This parameter will be calculated for patients with treatment-induced ADA and treatment-boosted ADA.
- Peak titer (PEAKTIT): the highest titer observed for the subject.
- Time to peak titer (TPEAKTIT): the time to reach peak titer will be calculated by: the date of first peak titer observed first dose date +1.
- Total number of ADA Positive Samples (NOPOSAMP): the total number of ADA samples being confirmed positive for the subject.
- Total number of ADA Samples evaluated (NOADASAMT): the total number of ADA samples being collected and analyzed successfully with reportable results for the subject.

Lastly, subjects with positive ADA status may further be classified as being transient or persistent ADA response, if there are sufficient number of subjects with transient ADA status. Transient and persistent ADA definitions are defined below and based on (Shankar *et al.* 2014):

Transient ADA response:

- Treatment-induced ADA detected only at one sampling time point during the treatment or follow-up observation period (excluding the last sampling time point, which will be considered persistent unless shown to be undetectable at a later time) or
- Treatment-induced ADA detected at two or more sampling time points during the treatment (including follow-up period if any), where the first and last ADA-positive samples (irrespective of any negative samples in between) are separated by a period less than 16 weeks, and the subject's last sampling time point is ADA-negative.

Persistent ADA response:

- Treatment-induced ADA detected at two or more sampling time points during the treatment (including follow-up period if any), where the first and last ADA-positive samples (irrespective of any negative samples in between) are separated by a period of 16 weeks or longer or
- Treatment-induced ADA detected only at the last sampling time point of the study treatment period or at a sampling time point with less than 16 weeks before an ADA-negative last sample.

The subject level ADA prevalence, incidence, and positive ADA response being transient or persistent (if applicable) will be calculated as the total number of and percentage of evaluated patients with IM negative, positive, and unknown status by treatment and dose. Subject level IM parameters (as described above), if applicable, will be listed by treatment and dose for all evaluable subjects, and also appropriately summarized (using descriptive statistics) as median, quartiles (25% and 75%) and range, by treatment and dose.

